3.2 Randomization and Masking

This is a single-arm, open-label study, no randomization and masking will be applied.

Figure 1 Study Flow Chart

3.3 Sample Size Planning

A total of 33 subjects was planned to be enrolled to obtain 30 completed subjects in this study. The sample size for this proof-of-concept study was not calculated based on statistical considerations. Clinical judgment and experience were the basis for determining the number of subjects needed to achieve study goals.

3.4 Visits and Assessments

The study period will include the initial Screening Visit, the 2-week wash-out phase, and the 3month open-label study treatment phase encompassing the Baseline, Month 1, Month 2 and Month 3 study visits. The schedule for all study-related procedures for all evaluations is shown in Table 1.

Table 1Schedule of Study Procedures

	Wash out period Open-label study treatment Period				Unscheduled Visit /	
Study procedures	Screening Day -14 ± 3	Baseline Day 1	Month 1 Day 28 ± 3	Month 2 Day 56 ± 3	Month 3 Day 84 ± 7	premature study discontinuation
Informed consent	Х					
Demographic information	Х					
Ocular and systemic medical history	х	Х				
Previous and Concomitant ocular and systemic medications (incl. concomitant artificial tear usage)	х	х	x	x	x	X ⁴
Inclusion/exclusion criteria	Х	Х				
Efficacy Assessments						
Tear break up time (TBUT)	Х	Х	Х	х	x	X ⁴
Corneal fluorescein staining (Modified Oxford Scale)	Х	х	x	x	х	X ⁴
Schirmer test (without anaesthesia)		х			x	X ⁴
Functional visual acuity (FVA parameters, FVA system)	х	х	x	x	x	X ⁴
Objective scatter index (OSI) (double-pass aberrometer)	х	х	x	x	x	X4
RMS/Higher-order aberrations (Hartmann-Schack aberrometer)	х				x	X4
Investigator global evaluation					X	X ⁴
Patient global evaluation					X	X ⁴

	Wash out period		Open-label study	treatment Period	ł	Unscheduled Visit /
	Screening	Baseline	Month 1	Month 2	Month 3	premature
Study procedures	Day –14 ± 3	Day 1	Day 28 ± 3	Day 56 ± 3	Day 84 ± 7	study
						discontinuation
Visual Analog Scale (VAS)	X 1	X 1	X ¹	X 1	X 1	X ^{1,4}
(photophobia, blurred vision)	~	X	~	X	^	~
Safety Evaluations						
Slit lamp examination	Х	Х	х	х	Х	X ⁴
Uncorrected distance visual	v	v	v	v	×	v ⁴
acuity (UDVA in LogMAR)	^	^	^	^	^	^
Best corrected distance visual	x	v	×	×	×	Y ⁴
acuity (BCDVA in LogMAR)	^	^	~	^	^	^
Dilated fundus examination		Х			Х	X ⁴
Intraocular Pressure (IOP)		х			Х	X ⁴
Urine pregnancy test (women	x	X ³			x	¥2
of childbearing potential only)	~	X			~	^
Confirm patient discontinued	x					
treatment related to dry eye	~					
Adverse events (AEs)		Х	х	х	Х	X ⁴
Treatment Procedures						
Dispense study medication and	v ²	V ²	v ²	y ²		
unpreserved artificial tears	^	Λ	^	^		
Collection of used study						
medication and unpreserved		х	х	х	Х	X4
artificial tears						

ET/EOT=early termination/end of treatment.

1 VASs should be performed at the beginning of the visit before medical history and any study assessment.

2 Dispense unpreserved artificial tears. Instruction: to be instilled up to eight times per day in each eye

3 Only for patients fulfilling criteria for severe keratitis that will be included.

4 Assessments to be performed during unscheduled visits only in case of premature discontinuation

4 DEFINITIONS

4.1 Time-Related Terms

4.1.1 Screening Visit (Day -14 ± 3 days)

The *Screening Visit* is the visit when the subject will be screened in accordance with the protocol-defined inclusion and exclusion criteria. It will be performed within 14 days prior to the first dose of the study medication administration.

4.1.2 Baseline Visit (Day 1)

The *Baseline Visit* is the Day 1 visit when the subject will receive the first dose of the study medication.

4.1.3 Analysis Period and Treatment Start and End Dates

There will be only one analysis period for this study:

Analysis Period	Analysis Period Start Date	Analysis Period End Date	
Open-label treatment period	The date of the first dose of the study medication administration	The Study Exit date	

4.1.4 Study Day

The *study day* describes the relative day of an observation starting with the reference date. For this study, the treatment start date is the reference date and the *study day* will be calculated as:

- For days prior to the treatment start date, Study Day = Date Treatment Start Date
- For days on/after the treatment start date, Study Day = Date Treatment Start Date + 1

Note that there is no Study Day 0.

4.1.5 Out-of-Window Measurements, Analysis Visit, and Analysis Window

For this study, a measurement collected at a visit is an *out-of-window* measurement if the study day of the visit falls outside of a visit window specified in Assessment Schedule (Table 1; otherwise, it will be treated as a *within-window* measurement.

Analysis visit is a timing variable to be used for analyses involving visits. For each analysis visit, an analysis window is set up to determine the analysis visit to which a measurement should be mapped. The *analysis window*, which is wider than the visit window, will be employed to minimize the amount of missing data for analysis purposes.

Post-baseline Visit (Target Assessment Date)	Visit Window	Analysis Window
Month 1 (Day 28)	[25, 31]	[21, 48]
Month 2 (Day 56)	[53, 59]	[49, 76]
Month 3 (Day 84)	[77, 91]	[77, 104]

The analysis visit of a measurement will be determined based on the study day of the measurement and specified analysis windows, and it is not necessarily the same as the study visit at which the measurement was collected. For example, an out-of-window measurement collected at the Month 2 study visit will be mapped to the Month 3 analysis visit, if the study day of the measurement falls into the analysis window of Month 3.

For analyses involving post-baseline visits, if there are two or more measurements that fall into the same analysis window of a post-baseline visit, then the measurement closest to the target assessment day will be selected for that visit. In the case that two measurements are closest and equidistant to the target assessment day, i.e., one is before and one is after the target assessment day, the later one will be selected for that visit.

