## 9.3.3 Unscheduled Visit/Premature Discontinuation

An unscheduled visit may be performed as needed between two scheduled visits. The reason for the visit will be recorded on the eCRF. The examinations required at an unscheduled visit will be at the discretion of the investigator.

If necessary, (e.g. to follow up an AE), the investigator may schedule further "unscheduled" visits at his/her discretion. Data from an unscheduled visit will not be collected in the eCRF with the exception of information related to an AE or the follow-up of an AE.

In case of premature study discontinuation between two scheduled visits, the Unscheduled Visit Form and the Exit Forms will be completed. If the premature discontinuation occurs during an Unscheduled Visit prior to Month 3, the investigator will complete and record all of the exams scheduled at the Month 3 Visit on the Unscheduled Visit Form. In case of premature study discontinuation, the investigator will ensure that all used and unused study medication for the study period has been collected from the patient.

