4.4.2.5 Intraocular Pressure (IOP)

IOP will be measured using Goldman applanation tonometry (one measurement) at the Baseline and Month 3/early termination visits.

A decrease in IOP indicates improvement in the intraocular pressure.

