6.2.2 Safety Endpoints

Descriptive summaries of safety measures will be based on observed data only. No imputation of missing scores will be implemented.

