9.2 Slit-lamp Biomicroscopy

For each biomicroscopy parameter rated on a 0-3 scale (0=None, 1=Mild, 2=Moderate, or 3=Severe) or 0-4 scale (0=None, 1=Mild, 2=Moderate, 3=Severe, and 4=Very severe), rating scores and shift from baseline will be summarized by analysis visit for the analysis eye and the fellow eye, separately. In addition, any worsening (increase) of ≥ 2 units from baseline will be listed.

For lashes, which are collected as Normal or Abnormal, rating scores and shift from baseline in status will be summarized by analysis visit for the analysis eye and the fellow eye, separately. Any worsening in status from Normal at baseline to Abnormal after baseline will be listed.

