9.6 Intraocular Pressure

IOP and change from baseline in IOP will be summarized by analysis visit for the analysis eye and the fellow eye, separately. Subjects with any increase of ≥ 10 mmHg in IOP at any follow-up visit will be listed.

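### The SAP's visit-window rule leaves early-termination exams on Days 2-20 out of every by-visit ocular safety table, and drops most later slit-lamp, UDVA and BCDVA exams at withdrawal

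*SAP*

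**What the plan says.** Protocol 9.3.3 collects a complete examination at withdrawal. If a patient stops at an unscheduled visit before Month 3, "the investigator will complete and record all of the exams scheduled at the Month 3 Visit on the Unscheduled Visit Form".

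SAP 4.1.5 then decides where each result goes: "The analysis visit of a measurement will be determined based on the study day of the measurement and specified analysis windows". The analysis windows are [21, 48] for Month 1, [49, 76] for Month 2 and [77, 104] for Month 3. One value per window is kept. If several fall in a window, "then the measurement closest to the target assessment day will be selected for that visit"; on an exact tie, "the later one will be selected for that visit". Nothing in the section treats ET measurements differently.

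The safety tables follow these windows. For slit lamp (SAP 9.2), "rating scores and shift from baseline will be summarized by analysis visit for the analysis eye and the fellow eye, separately". For IOP (SAP 9.6), "IOP and change from baseline in IOP will be summarized by analysis visit for the analysis eye and the fellow eye, separately". UDVA, BCDVA and dilated fundus (SAP 9.3-9.5) are handled the same way. SAP 6.2.2 rules out imputation: "Descriptive summaries of safety measures will be based on observed data only". No table has a last-value, worst-value or ET row.

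The measures differ in schedule. Slit lamp, UDVA and BCDVA are done at every visit. IOP and fundus are not: "IOP will be measured using Goldman applanation tonometry (one measurement) at the Baseline and Month 3/early termination visits", and SAP 4.4.2.4 gives the same schedule for fundus.

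**The concern.** Ocular tolerability and safety are a stated secondary objective, and the ET examination is the last look at the eye of a patient who leaves. Under the rule that examination can be missing from the tables or give way to an earlier one.

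- A patient leaving on Day 10 can be in the Safety population (one dose plus any follow-up information) and yet add no post-baseline value to any of the five summaries. SAP 4.1.5 says its windows are wide in order to limit missing data; before Day 21 they create it.
- A patient seen on Day 28 who leaves on Day 40 is represented at Month 1 by the Day 28 slit lamp and acuities. The Day 40 results appear in no by-visit table.
- A Day 40 IOP or fundus result is tabulated under Month 1, where neither test is scheduled, and not with the Month 3 results that the endpoint names.

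**Working it through.** **The plan's own figures.** Target day plus or minus the scheduled tolerance gives 28 ± 3 = [25, 31], 56 ± 3 = [53, 59] and 84 ± 7 = [77, 91], which match SAP 4.1.5. Each analysis window runs from target − 7 to target + 20 (28 days). Together they cover Days 21-104 without a gap, so nothing covers Days 2-20. The documents give no count of ET exams left out, so there is no such figure to reproduce.

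**Assumptions, not in the documents.** ET is equally likely on each of Days 2-83 that is not a scheduled visit day. In the base case, Months 1 and 2 were attended on Days 28 and 56.

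**Slit lamp, UDVA, BCDVA, base case.** Possible ET days: 82 (Days 2-83) − 2 visit days = 80.

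| ET day | Days | Result under SAP 4.1.5 |
|---|---|---|
| 2-20 | 19 | no window, left out |
| 21-27 | 7 | before the Day 28 visit, kept |
| 29-48 | 20 | Day 28 visit is closer, left out |
| 49-55 | 7 | before the Day 56 visit, kept |
| 57-76 | 20 | Day 56 visit is closer, left out |
| 77-83 | 7 | Month 3 window, kept |

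Left out: 19 + 20 + 20 = 59, and 59/80 = 73.8%.

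**Varying the assumptions, same three measures.**

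- Visits on Days 25 and 53, or on Days 31 and 59: ET is lost on Days 32-48 and 60-76 (17 + 17 = 34). (19 + 34)/80 = 53/80 = 66.3%. Over all in-window visit days the range is 66.3% to 73.8%.
- ET counted only to Day 76: 53/73 = 72.6% to 59/73 = 80.8%.
- Month 1 missed: (19 + 20)/81 = 39/81 = 48.1%.
- Both visits missed: 19/82 = 23.2%.

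**IOP and fundus.** Nothing is measured at Month 1 or Month 2 to compete with an ET value, so only Days 2-20 are left out: 19/82 = 23.2%. Values on Days 21-76 are kept under Month 1 or Month 2; values on Days 77-83 already fall under Month 3.

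**What the other outputs recover.** The listings are worded as any worsening, after baseline, or at any follow-up visit, and none is tied to the selected analysis-visit value.

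| Measure | Listed | Not listed |
|---|---|---|
| Slit lamp grades | worsening of 2 or more units | 1-unit worsening |
| Lashes, fundus | any Normal to Abnormal | – |
| BCDVA | score of 2.0 or more, or change of 0.30 LogMAR or more | loss under 0.30 with score under 2.0 |
| IOP | rise of 10 mmHg or more | smaller rise |
| UDVA | no listing | all change |

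Conjunctival erythema is graded 0-3, so a move from 2 to the maximum of 3 cannot reach the 2-unit threshold.

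**After the fix.** A row using every recorded post-dose exam leaves out 0 of 80 days for slit lamp and acuity (now 59) and 0 of 82 for IOP and fundus (now 19).

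**The case against.** The strongest reply is that withdrawal findings are reported elsewhere. Treatment-emergent adverse events are defined by date and do not depend on the windows. Events leading to discontinuation are tabulated and listed, and the listings catch large changes and any fundus or lash change from normal to abnormal. An intolerance that makes a patient leave should therefore be visible. This stands, and it limits the loss to graded or measured change below the thresholds, plus UDVA.

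A reader might infer that the rule discards most ET results for all five measures. The documents do not support that: IOP and fundus have no competing value and lose only Days 2-20. Labelling a Day 40 IOP by its actual time is accurate as far as it goes, and moving it to a Month 3/ET row mixes exposure durations. That is a presentation choice to be footnoted.

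A reader might also infer that patients leave mostly for intolerance and that the retained earlier exam looks better. Neither has a source. Protocol 7.4 lists nine withdrawal reasons, and a patient lost to follow-up may have no ET exam. A patient who stops at a scheduled visit loses nothing through the closest-to-target rule.

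The study is also small, single-arm and exploratory, with no statistical testing of safety measures, so few patients may be affected. That bears on priority; the rule still works as described.

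**Conclusion.** The point holds in limited form. Followed as written, SAP 4.1.5 leaves ET exams on Days 2-20 out of the by-visit tables for all five measures. It also drops later ET slit-lamp, UDVA and BCDVA exams when the scheduled visit in the same window was closer to target.

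For those three measures, 74% of possible ET days are affected in the base case. The range is about 66-81% with both visits attended in window, 48% with Month 1 missed and 23% with both missed. These are shares of days. They become shares of patients only if withdrawal is equally likely on each day, and the documents give no withdrawal timing.

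The number of patients is unknown. SAP 3.3 plans 33 enrolled for 30 completed; applying 3/33 to the 17 enrolled gives 17 × 3/33 = 1.5. This is an assumption, because the protocol summary says 30 included, so the 3 could be wash-out failures who never received drug. One patient would be 1/17 = 5.9% of those enrolled.

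It would go too far to say that withdrawal findings disappear from the safety output. What the summaries and listings lose at withdrawal is slit-lamp worsening under 2 units, BCDVA loss under 0.30 LogMAR (score below 2.0) and all UDVA change. For IOP, a rise under 10 mmHg is lost only on Days 2-20. This is a cheap improvement.

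**What to change.** 1. In SAP 9.2-9.6, add two rows per eye and parameter, each with change or shift from baseline: the last on-treatment value (Month 3 or ET), and the worst post-baseline value over all recorded post-dose exams including ET.
2. In SAP 4.1.5, state that the closest-to-target selection applies neither to these rows nor to the listings, which use all post-dose data.
3. Present IOP and fundus as Month 3/ET, with a footnote that exposure durations are mixed. SAP 8.2.2 already pools Month 3 and ET for the two global evaluations.
4. Leave other unscheduled-visit data out of these rows. Protocol 9.3.3 does not collect them in the eCRF, except for information related to an adverse event.

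The cost is SAP wording and two rows per safety table, with no new data. The only downside is the mix of exposure durations, which the footnote covers.

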4.1.6 Extent of Exposure

The *extent of exposure* to study medication will be assessed by duration of treatment exposure, which will be derived using the following formula:

Duration of treatment exposure = (Treatment end date – Treatment start date) + 1

4.1.7 Duration of Quitting Smoke

For ex-smokers, the *duration of quitting smoke* will be derived using the following formula:

Duration of quitting smoke = (Date of Screening Visit – Smoking stop date) + 1

4.2 Endpoint-Related Definitions

4.2.1 Analysis Eye and Fellow Eye

The *analysis eye* of an enrolled subject is defined as the eligible eye, the eye that fulfills all the criteria listed under the inclusion criteria #4. If both eyes are eligible, the eye with the highest baseline CFS score will be chosen. If both eyes have the same CFS score, the eye with the lowest baseline VMR will be chosen. If VMR values are the same for both eyes, the right eye will be chosen. The *fellow eye* is the non-analysis eye.

4.2.2 Baseline Score

For any measure, the *baseline score* is the last observed measurement prior to the first dose of the study medication. If any variable is missing a value on Day 1, values from the Screening

Visit will be used to impute the baseline score, i.e., the last observation carried forward (LOCF) approach will be used.

4.2.3 Change from Baseline

The change from baseline in a measure at a post-baseline visit will be derived as:

Change = (Score at the Post-Baseline Visit) – (Baseline Score)

4.3 Efficacy-Related Definitions

4.3.1 Functional Visual Acuity (FVA) Parameters

Functional Visual Acuity (FVA) parameters will be obtained from the FVA measurement system at each scheduled visit and at the premature study discontinuation visit. FVA parameters assess dynamic visual acuity over a period of 60 seconds. Measurements will be made under natural blinking conditions without topical anesthesia.

FVA parameters include:

- **FVA**: FVA is the mean value of time-wise change of visual acuity measured using the FVA measurement system during the overall examination period (60 seconds). It is measured under the natural blinking state without topical anaesthesia and expressed in decimal notation.
- LogMAR FVA: LogMAR FVA is FVA converted to LogMAR notation. LogMAR FVA will be the variable used for all the analyses (instead of FVA). A decrease from baseline in LogMAR FVA indicates improvement.
- Visual Maintenance Ratio (VMR): VMR is an objective index for evaluating changes of dynamic vision from baseline visual acuity. It is defined as the ratio of LogMAR FVA over the 60 seconds divided by the value of Starting LogMAR VA. An increase from baseline in VMR indicates improvement.
- Starting VA and Starting LogMAR VA: Starting VA is the baseline visual acuity for a 60-second examination period; it is the value of the best corrected visual acuity measured by the FVA measurement system at the beginning of the 60-second examination period. Starting LogMAR VA is Starting VA converted to LogMAR notation.
- **Minimal VA and Minimal LogMAR VA**: Minimal VA is the lowest visual acuity recorded during the 60-second examination period. Minimal LogMAR VA is Minimal VA converted to LogMAR notation.
- **Maximal VA and Maximal LogMAR VA**: Maximal VA is the highest visual acuity recorded during the 60-second examination period. Maximal LogMAR VA is Maximal VA converted to LogMAR notation.

4.3.2 **Objective Scatter Index (OSI)**

OSI and its variance will be measured using a double-pass aberrometer at each scheduled visit and at the premature study discontinuation visit. OSI is an objective way to assess the intensity of the subjective visual disturbances.

A decrease from baseline in OSI or its variance indicates improvement.

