## Appendix A-IV Functional Visual Acuity (Kaido 2013).

The functional visual acuity (FVA) will be measured using FVA measurement system (AS-28; Kowa, Aichi, Japan) at each study visit. The changes with time in the continuous visual acuity using the Landolt optotypes (Figure 2) with their sizes change depending on the correctness of the responses.

The optotypes are displayed automatically, starting with smaller ones. When the response is correct, even smaller optotypes are presented. If the responses are incorrect, larger optotypes are presented automatically (Figure 3). Visual acuity is continuously measured from the baseline best corrected Landolt visual acuity. The functional visual acuity measurement system can measure visual acuity from 150/100 to 20/200. When there is no response within the set display time, the answer is assumed to be an error, and the optotype enlarged automatically.

The outcomes will be recorded as starting visual acuity, LogMAR functional visual acuity, visual maintenance ratio, and maximal and minimal visual acuities:

- Starting visual acuity is defined as the baseline visual acuity, which is the value of the standard best corrected visual acuity measured by the functional visual acuity measurement system
- Functional visual acuity is defined as the mean value of time-wise change of the visual acuity during the overall examination
- Visual maintenance ratio (VRM) is calculated as follows (Kaido 2006, Kaido 2011):

visual maintenance ratio = (lowest LogMAR visual acuity score –functional visual acuity

at 60 s)/(lowest LogMAR visual acuity score – baseline visual acuity)

An increase in VMR from baseline will indicate an improvement.

• Maximal and minimal visual acuities are defined as the highest and lowest visual acuities recorded during the examination.

**Figure 2** Presentation of Landolt optotypes on mini-pointer of the functional visual acuity device (Kaido 2013).

Figure 3 flowchart diagram of optotypes during functional visual acuity testing (Kaido 2013).

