2.2.1 Primary Efficacy Endpoints

The primary efficacy endpoints are:

- Correlation between the change from baseline in VMR measured with FVA system at Month 3 and the change from baseline in the CFS at Month 3.
- Correlation between the change from baseline in variance of OSI measured with double pass aberrometer at Month 3 and the change from baseline in the CFS at Month 3.

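### SAP 4.3.1 defines VMR as a ratio of LogMAR values that is undefined at a 20/20 start and, at a fixed start worse than 20/20, falls as vision improves; whether results are affected depends on an unsettled point, device-read or derived

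*SAP*

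**What the plan says.** SAP 4.3.1 defines VMR in these words: "It is defined as the ratio of LogMAR FVA over the 60 seconds divided by the value of Starting LogMAR VA". The same section gives two directions. For FVA: "A decrease from baseline in LogMAR FVA indicates improvement". For VMR: "An increase from baseline in VMR indicates improvement". SAP 10.2 converts acuities by LogMAR = -log10(decimal VA).

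The protocol gives two other definitions.

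- Appendix A-IV has a formula that begins "visual maintenance ratio = (lowest LogMAR visual acuity score". In full, it is the lowest LogMAR score minus FVA at 60 s, divided by the lowest LogMAR score minus baseline acuity. No number is given for the lowest score. The appendix does give the device range: "The functional visual acuity measurement system can measure visual acuity from 150/100 to 20/200".
- Section 9.3.4.1 says VMR is to be calculated by dividing FVA by starting VA, and names no scale.

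On where the analysed value comes from, SAP 4.3.1 says FVA "parameters will be obtained from the FVA measurement system at each scheduled visit". The primary endpoint in SAP 2.2.1 reads "Correlation between the change from baseline in VMR measured with FVA system at Month 3". Appendix A-IV says "The outcomes will be recorded as starting visual acuity, LogMAR functional visual acuity, visual maintenance ratio". No sentence states outright that the analysed VMR is the device value and is not recomputed.

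**The concern.** VMR sits in the numerator of the trial's argument. Its change at Month 3 is one side of one of the two primary correlations (SAP 8.1.1), and it is the dependent variable of a sensitivity mixed model (SAP 8.1.2 and Appendix B).

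The SAP sentence puts a quantity that falls with improvement over a denominator that can be positive, zero or negative, and then says the result rises with improvement. That is true only for eyes that start better than 20/20. If a programmer derived VMR from the sentence, eyes starting at exactly 20/20 would drop out, eyes close to it would take extreme values, and eyes on either side would move in opposite directions for the same clinical change. With 17 patients enrolled (SAP 3.1), neither lost observations nor mixed signs would be minor.

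**Working it through.** **Inputs.** LogMAR = -log10(decimal VA), from SAP 10.2. Device range 150/100 to 20/200, from Appendix A-IV: decimal 1.5 to 0.1, or LogMAR -0.176 to 1.0, so LogMAR 0 lies inside it. Entry rule VMR <0.95, from Protocol 7.1. The documents give no VMR value to reproduce, so the check is algebra on chosen acuities.

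**Formulas.**

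- SAP 4.3.1: LogMAR FVA / LogMAR start.
- Appendix A-IV: (c - LogMAR FVA) / (c - LogMAR start), where c is the lowest LogMAR score. c = 1.0 is implied by the device range; 1.3 and 2.0 are illustrative.

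**Direction at a fixed start of 0.8 (LogMAR 0.0969), FVA improving from 0.5 (0.3010) to 0.7 (0.1549).**

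- SAP: 0.3010/0.0969 = 3.11, then 0.1549/0.0969 = 1.60. It falls.
- Appendix A-IV, c = 1.0: 0.6990/0.9031 = 0.774, then 0.8451/0.9031 = 0.936. It rises.
- Appendix A-IV, c = 1.3: 0.830 to 0.952. With c = 2.0: 0.893 to 0.970. The direction does not depend on which of these is used.

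**Same gain, different starts.** For a 0.1 LogMAR improvement in FVA at a fixed start, the SAP ratio changes by -0.1/(LogMAR start) and Appendix A-IV by 0.1/(c - LogMAR start).

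| Start (decimal) | Change in SAP ratio |
|---|---|
| 0.5 | -0.33 |
| 0.8 | -1.03 |
| 0.95 | -4.49 |
| 1.0 | undefined |
| 1.05 | +4.72 |
| 1.2 | +1.26 |

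Appendix A-IV with c = 1.0 changes by +0.14 at a start of 0.5 and +0.09 at 1.2.

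**Instability in level.** At FVA 0.8, starts of 0.95, 1.0 and 1.05 give SAP values of 4.35, undefined and -4.57. Appendix A-IV (c = 1.0) gives 0.92, 0.90 and 0.88.

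**Entry rule.** At a start of 0.8, a SAP ratio below 0.95 needs LogMAR FVA below 0.95 x 0.0969 = 0.0921, which is FVA above 0.809. The eye would have to average better than its own start. An eye that started worse than 20/20 and lost acuity over the test would score above 1 and fail the criterion. The SAP ratio therefore cannot be the quantity behind the entry rule.

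**Meaning of the lowest score.** If it is read as the smallest number (150/100, c = -0.176), Appendix A-IV also runs backwards: (-0.176 - 0.3010)/(-0.176 - 0.0969) = 1.75, falling to 1.21. The constant has to be stated.

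**Sign of the correlation, if VMR were derived.** A simulation of 17 patients used assumed inputs: fixed starts, CFS changes of 0 to -3, and an FVA loss that shrinks by 0.04 LogMAR per CFS grade with noise SD 0.03. Mean Spearman correlations were:

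- all starts worse than 20/20: +0.68 (SAP) against -0.81 (Appendix A-IV);
- all better: -0.71 against -0.82;
- mixed: +0.15 against -0.81.

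These show sign only and do not predict this trial's values.

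**The case against.** The best answer is that nobody would compute VMR this way. SAP 4.3.1 and 2.2.1, Protocol 9.3.1.1 and Appendix A-IV all treat VMR as a device output. SAP 10.2 leaves it off the list of fields to convert, the Appendix B code takes VMR change as given, and eligibility needed VMR before conversion took place at the analysis stage. The study is declared exploratory, with no formal hypothesis testing. On that view this is an erratum with no effect on any result.

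Most of that stands, and it limits the point. It does not remove it: Protocol 9.3.4.1 says VMR is to be calculated, Appendix A-IV also presents a calculation, and an analyst told to follow the SAP has a written formula that fails.

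Three stronger readings are not supported.

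- A reader might infer that the primary VMR result is reversed. The documents do not show that VMR is derived, and they give no distribution of starting acuity, so how many eyes would be affected even then is unknown.
- A reader might say the ratio falls with improvement in every eye starting worse than 20/20. That holds only with starting VA fixed, and starting VA is measured afresh at each examination. If the start moves from 0.5 to 0.8 and FVA from 0.4 to 0.5, the SAP ratio rises from 1.32 to 3.11. Appendix A-IV falls from 0.86 to 0.77, so the two still disagree.
- A reader might call this an undeclared change from the protocol. The SAP cites protocol version 3.0 and the text compared here is version 4.0, so that cannot be claimed. The protocol also disagrees with itself, and its 9.3.4.1 wording is close to the SAP's with the scale left out.

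**Conclusion.** The SAP 4.3.1 sentence is wrong as written, with high confidence. It contradicts the section's own directions for eyes starting worse than 20/20 at a fixed start, has no value at a 20/20 start, cannot be what the entry criterion uses, and differs from Appendix A-IV. None of this depends on choosing among c = 1.0, 1.3 and 2.0; it does rest on the lowest score meaning the worst acuity.

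The effect on results is conditional. If VMR is device-read, which the documents favour but do not settle, it is nil. If VMR is derived by the SAP ratio, the primary VMR-CFS Spearman correlation and the mixed model could lose observations or have scrambled or reversed signs. This should be fixed before analysis because the variable is primary and the correction is small.

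**What to change.** Before analysis:

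1. Replace the SAP 4.3.1 sentence with the Appendix A-IV formula on LogMAR values. State that the lowest score means the worst measurable acuity. The device range implies 20/200, or 1.0 LogMAR; confirm this against the device documentation.
2. State that the analysed VMR is the device-recorded value and is not recomputed with the LogMAR ratio.
3. Reconcile SAP 4.3.1, Protocol 9.3.4.1 and Appendix A-IV, including FVA at 60 s in the appendix formula against the mean over 60 seconds elsewhere. Record the correction in SAP section 10.
4. Optionally, compare recorded VMR with the formula as a data-quality check. SAP 10.2 reports confusion over which device numbers to record, which gives this some value. Wait until the constant and the averaging scale (decimal or LogMAR) are confirmed, and settle how SAP 10.1, where FVA was not a device output, fits with 10.2, where decimal scores were recorded. Query only large discrepancies, since small ones could come from these unknowns.

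A sensitivity analysis on a derived VMR is not needed. The cost is a corrected sentence, a source statement, a reconciliation of three definitions and a section 10 entry. The optional check may raise a few site queries. The primary endpoint, entry criteria and analysis populations stay as they are.
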